#### 5.7.4. Analysis of Primary Efficacy Endpoint

The proportion of subjects alive and free of ventilation at Day 29 for Cohort 1, and the proportion of subjects who die (mortality rate) by Day 29 for Cohort 2 will be analyzed by the CMH test adjusted for the actual randomization strata (Cohort 1: standard of care antiretroviral therapy, age, and ARDS status; Cohort 2: standard of care antiretroviral therapy and age). The 95% confidence interval (CI) will be calculated using the Clopper-Pearson exact method. Number of subjects and percentages will be summarized by treatment.

The CMH method addresses the global null hypothesis of no difference between treatments. Hence, it corresponds to the risk difference being 0, the risk ratio being 1, and the odds ratio being 1. The CMH

p-value is the same across odds ratio/risk ratio/risk difference. In addition to CMH p-value, the stratified risk difference, stratified relative risk, and the stratified odds ratio and their 95% confidence interval (CI) will be provided in our analyses.

Analysis of the primary efficacy endpoint based on the per-protocol population will be conducted following the same methods.

## **5.7.5. Analysis of Secondary and Other Efficacy Endpoints**

### **5.7.5.1. Time to event endpoints**

For all time to event endpoints, the primary treatment comparison between the active treatment and the placebo (10 mg/kg mavrilimumab vs. placebo, and 6 mg/kg mavrilimumab vs. placebo) will be based on log-rank test stratified by the actual randomization strata.

The Kaplan-Meier (KM) method will be used to estimate the survival distribution function for all the time to event endpoints. The 25th, 50th (median), 75th percentiles and their two-sided 95% confidence interval (CI) will be estimated. In addition, the probability of favorable outcome (event rates, or event-free rates depending on the endpoints) at Day 4, 8, 15, 22, 29, 60, and 90 will be calculated as appropriate, along with their standard errors using Greenwood's formula (Klein, 2003) stratified by the actual randomization strata. Corresponding Kaplan-Meier plot will be produced. In case of favorable outcomes, the plot will be based on 1 - KM estimate.

The hazard ratio for (10 mg/kg mavrilimumab vs. placebo) or (6 mg/kg mavrilimumab vs. placebo) and the corresponding Wald 95% CI will be calculated based on a Cox proportional-hazards model with treatment as covariates, stratified by the actual randomization strata.

### **5.7.5.2. Binary (rate or proportion) endpoints**

The primary treatment comparison for all binary endpoints will be based on the CMH test adjusted by actual randomization strata. Number of subjects and percentages will be summarized by treatment. The stratified risk difference, stratified relative risk, and the stratified odds ratio and their 95% CIs along with the CMH p-value will be provided in these analyses.

The event rates (or event-free) from the corresponding time to event analysis can serve as supportive analyses. For example, proportion of subjects with K-point clinical improvement can be estimated from time to K-point clinical improvement; mortality rate can be estimated from the overall survival. No formal testing will be conducted.

### **5.7.5.3. Endpoints to be summarized descriptively**

Descriptive statistics (n, mean, standard deviation, median, minimum, and maximum) will be used to summarize the following endpoints. No imputation will be done unless otherwise specified.

- [REDACTED]
- [REDACTED]
- [REDACTED]
- [REDACTED]
- [REDACTED]

[REDACTED]	
■	[REDACTED]
■	[REDACTED]
■	[REDACTED]
■	[REDACTED]
■	[REDACTED]
■	[REDACTED]
■	[REDACTED]
■	[REDACTED]
■	[REDACTED]
■	[REDACTED]

#### 5.7.6. Subgroup analysis

Subgroup analyses will be conducted for each of the randomization stratum for the primary efficacy endpoint and secondary endpoints.

### 5.8. Safety Analysis

The safety endpoints will be tabulated by treatment based on the Safety Analysis Set. All safety data including those collected during the safety follow-up will be listed by subject.

#### 5.8.1. Adverse Events

An adverse event (AE) is any untoward medical occurrence in a subject or clinical investigation subject administered a pharmaceutical product. An AE does not necessarily have a causal relationship with this treatment. An AE will be defined as treatment-related if its relationship to the study drug is reported as Possibly Related or Definitely Related by Investigator.

An AE is considered treatment-emergent adverse event (TEAE) if the AE begins on/after and within 90 days of the study drug administration. If the date of AE onset is missing or coincides with the date of the study drug administration and AE time is not captured, AE will be considered treatment emergent.

All AEs will be coded using MedDRA version 23.0. A subject experiencing multiple AEs under the same preferred term (PT) or same system organ class (SOC) will be counted only once for that PT or SOC by maximum severity. If a subject experience the same AE more than once with more than one causal relationship to study drug, the strongest causal relationship to study drug will be given precedence. Any missing severity, causality, or outcome will not be imputed and classified as 'Missing'. Detailed imputation rules for missing AE dates are in Section 8.1.1.

An adverse event of special interest (AESI) is one of scientific and medical interest specific to understanding of the Investigational Product and requires close monitoring and rapid communication by the investigator to the sponsor. An AESI may be serious or non-serious.

The number of subjects with at least one TEAE will be tabulated. The following tables summarize incidences of various aspects of TEAEs, treatment-emergent serious AEs (TESAEs), and treatment-emergent AESIs (TEAESIs):

- Overview of TEAEs (summary of all the subsequent items)
- TEAEs by SOC and PT
- TEAEs by PT
- TEAEs by maximum severity (mild, moderate, or severe)
- Drug related TEAEs (related or not related) by SOC and PT
- TESAEs by SOC and PT
- Drug related TESAEs by SOC and PT
- TESAEs by PT
- TEAESIs by SOC and PT
- TEAEs leading to dose interruption by SOC and PT
- TEAEs leading to death by SOC and PT

All information pertaining to adverse events will be listed by subject, detailing verbatim term given by the investigator, preferred term, system organ class, start date, stop date, severity, outcome, action taken and drug relatedness.

Separate listings will be created for Serious TEAEs, and TEAESI, and death.

Additionally, non-serious TEAEs by SOC and PT will be tabulated.

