## **12.2. Adverse and Serious Adverse Events**

### **12.2.1. Definition of Adverse Events**

#### **12.2.1.1. Adverse Event (AE)**

An AE is any untoward medical occurrence (eg, any unfavorable and unintended sign [including abnormal laboratory findings], symptom or disease) in a clinical investigation subject after providing written informed consent for participation in the study. Therefore, an AE may or may not be temporally or causally associated with the use of a medicinal (investigational) product.

Abnormal laboratory values or test results constitute AEs only if they fulfill at least one of the following criteria:

- they induce clinical signs or symptoms
- they are considered clinically significant
- they require therapy

Clinically significant abnormal laboratory values or test results must be identified through a review of values outside of normal ranges/clinically notable ranges, significant changes from baseline or the previous visit, or values, which are considered non-typical in subjects with the underlying disease.

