## Serious Infection

Infections meeting SAE criteria (eg, required hospitalization) or infections with a severity grade of “severe” that require treatment with IV therapy (antibiotics, antiviral, or antifungal) and opportunistic infections will be considered AESI and should be reported within 24 hours of knowledge of the event.

Every effort should be made to identify the causative pathogen through prompt and appropriate investigation by the Investigator or reporting physician.

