### **12.4. Recording Adverse Events**

The Investigator has the responsibility for managing the safety of individual subject and identifying AEs.

Qualified medical personnel will be readily available to advise on trial related medical questions or problems.

The occurrence of AEs must be sought by non-directive questioning of the subject at each visit during the study. AEs also may be detected when they are volunteered by the subject during or between visits or through physical examination findings, laboratory test findings, or other assessments.

AEs must be recorded in the Adverse Events CRF under the signs, symptoms or diagnosis associated with them, accompanied by the following information (as far as possible) (if the event is serious refer to Section 12.2.1.4):

1. The severity grade:
  - mild: usually transient in nature and generally not interfering with normal activities
  - moderate: sufficiently discomforting to interfere with normal activities
  - severe: prevents normal activities.
2. Its relationship to the study treatment. If the event is due to lack of efficacy or progression of underlying illness (ie, progression of the study indication) the assessment of causality will usually be 'Not suspected'. The rationale for this guidance is that the symptoms of a lack of efficacy or progression of underlying illness are not caused by the trial drug, they happen in spite of its administration and/or both lack of efficacy and progression of underlying disease can only be evaluated meaningfully by an analysis of cohorts, not on a single subject.
3. Its duration (start and end dates) or if the event is ongoing, an outcome of not recovered/not resolved must be reported.
4. Whether it constitutes a SAE (see Section 12.2.1.4 for definition of SAE) and which seriousness criteria have been met.
5. Action taken regarding with study treatment.

All AEs must be treated appropriately. This study includes a single IV dose administration. No dose adjustment is anticipated. Actions may include:

  - Not applicable
  - Dose temporarily interrupted but later completed
  - Dose interrupted and not completed
6. Its outcome
  - not recovered/not resolved
  - recovered/resolved
  - recovering/resolving
  - recovered/resolved with sequelae
7. fatal; or unknown.

Conditions that were already present at the time of informed consent should be recorded in the medical history of the subject.

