AEs (including lab abnormalities that constitute AEs) should be described using a diagnosis whenever possible, rather than individual underlying signs and symptoms.

AE monitoring should be continued for at least 60 days following the last dose of study treatment.

Once an AE is detected, it must be followed until its resolution or until it is judged to be permanent (eg, continuing at the end of the study), and assessment must be made at each visit (or more frequently, if necessary) of any changes in severity, the suspected relationship to the interventions required to treat it, and the outcome.

The Medical Dictionary for Regulatory Activities (MedDRA) will be used to code all AEs.

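### The TEAE definition has no worsening clause, so an AE that starts between consent and infusion and worsens after dosing can be left out of the by-arm AE tables

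*Combined protocol and SAP*

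**What the plan says.** The flag is set in Section 5.8.1 of the Phase 3 SAP: "An AE is considered treatment-emergent adverse event (TEAE) if the AE begins on/after and within 90 days of the study drug administration". Section 5.8.1 of the Phase 2 SAP has the identical sentence. Two defaults widen it. A missing onset date, or an onset on the dosing date with no clock time, counts as treatment-emergent. Under Section 8.1.1, a start date that lacks only the day and falls in the dosing month is set to the dose date. Neither SAP mentions worsening.

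The eleven AE tables listed in Phase 3 SAP 5.8.1 are all restricted to treatment-emergent events. A twelfth follows: "Additionally, non-serious TEAEs by SOC and PT will be tabulated". The special listings are mostly restricted too: "Separate listings will be created for Serious TEAEs, and TEAESI, and death". The general by-subject AE listing has no such restriction. Among its fields are "preferred term, system organ class, start date, stop date, severity, outcome, action taken and drug relatedness".

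AE collection starts before dosing. Protocol 12.2.1.1 covers untoward events "in a clinical investigation subject after providing written informed consent for participation in the study", and Table 2 marks AE collection at Screening. Protocol 12.4 sends only conditions already present at consent to medical history. The AE record carries a severity grade and "Its duration (start and end dates) or if the event is ongoing, an outcome of not recovered/not resolved must be reported". For an AE already detected, "assessment must be made at each visit (or more frequently, if necessary) of any changes in severity".

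**The concern.** A definition of this kind usually has two limbs: events that start after dosing, and events that start before dosing and get worse after it. Only the first is present here. The plan therefore creates AE records with pre-dose start dates and has no rule for counting them if they deteriorate after the infusion.

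Infection shows most clearly why this matters. Protocol Section 4 lists serious infection as an important potential risk of the drug, and Section 12.2.1.3 makes it an AE of special interest. That category covers "Infections meeting SAE criteria (eg, required hospitalization) or infections with a severity grade of" severe that need IV treatment, together with opportunistic infections. A mild infection starting the day before dosing may meet that description only after dosing, yet its onset date keeps it out of the special-interest table. Worsening of an infection after a single dose of an immunomodulator is an outcome that the comparison of arms ought to show.

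**Working it through.** **1. Length of the exposed window.** Footnote 1 to the Schedule of Activities allows screening up to 3 days before study drug. Protocol 6.1, the note under Table 4 and Phase 3 SAP 1.2 count the 3 days back from randomization. Footnote 10 allows up to 24 hours from randomization to the start of dosing. The window is therefore 3 days on the first reading and 3 + 1 = 4 days on the second. Against 90 days of follow-up, that is 3/(3 + 90) = 3.2% to 4/(4 + 90) = 4.3% of the time at risk. This is a share of time, not of events.

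**2. The rule applied to cases.** All cases assume that the event stays on one record. The worsening limb applies to the first four.

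| Onset and course | As written | With a worsening clause |
|---|---|---|
| 3 days before dosing, severe after | not a TEAE | TEAE |
| 1 day before dosing, serious after | not a TEAE | TEAE |
| 1 day before dosing, fatal after | not a TEAE | TEAE |
| Dosing date, recorded time before infusion, fatal after | not a TEAE | TEAE |
| Dosing date, no time recorded | TEAE | TEAE |
| Onset date missing | TEAE | TEAE |
| 1 day after dosing | TEAE | TEAE |

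The gap covers earlier calendar dates and dosing-day onsets with a recorded pre-infusion time. The rule uses clock time on the dosing day, so it does not rest on the date alone.

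**3. Where an excluded event is missing.** It is absent from the general TEAE tables and the severity table. As applicable, it is also absent from the serious, special-interest and fatal tables and from the serious and special-interest listings. It remains in the by-subject AE listing. If it is fatal, it also remains in the death listing and the mortality analyses.

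**4. Whether sites would keep one record.** Protocol 12.4 says to follow a detected AE to resolution and to assess changes in its severity. It does not say whether worsening should close one record and open another. Pulling the other way, Protocol 12.2.1.4 includes worsening of a pre-existing condition in the SAE definition, and the exceptions text in Section 12.5 requires all deaths and serious infections to be reported as SAEs. A new record with a post-dose onset would be counted under the current rule. The documents do not settle which happens.

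**5. What one omitted subject is worth in a table row.** Assume equal arms, all subjects dosed, and no other event for that subject in the row. In Phase 3 Cohort 1, 581/3 = 193.7 per arm and 1/193.7 = 0.52 percentage points. In Phase 3 Cohort 2, 63/3 = 21 per arm and 1/21 = 4.8 percentage points. These are unit conversions, not estimates of effect. The documents give no rate for such events.

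**The case against.** The strongest reply is that the loss depends on a recording practice that the protocol and SAPs do not establish. A worsening mild infection may well be re-recorded as a new diagnosis, such as sepsis, with its own post-dose onset. Protocol 12.4 asks for diagnoses rather than symptoms, and Phase 3 SAP 5.8.1 already allows for several records under one preferred term. This stands as a limit, but it also means that the flag depends on site habit, which a definition in the SAP should prevent.

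Infection is also a narrow route. Exclusion 5 in Protocol 7.2 lists uncontrolled systemic bacterial or fungal infection, and eligibility is confirmed again on Day 1 before dosing. Mainly controlled or local infections remain. Neutropenia and drug-induced liver injury are defined by laboratory thresholds and are unlikely routes. Safety is descriptive under Protocol 13.2.5, so no test is affected. All of this stands and reduces the size of the point.

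Three stronger readings are tempting, and the documents do not support them.

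- A reader might infer that the safety comparison is biased towards the drug. Onset before dosing in a randomized, blinded trial gives no such direction. The likely effect is under-counting, with some chance of missing a drug effect on worsening.
- A reader might count displays. A non-serious event is missing from 5 + 1 = 6 of the 12 tables, and a fatal, drug-related serious infection from 5 + 2 + 1 + 1 + 1 = 10. That is one event seen through overlapping tables and does not measure importance. The upper case also needs an event that began before dosing to be judged drug related.
- A reader might infer that deaths are lost. They are not. A mismatch between the fatal-TEAE table and the death listing could also arise from undosed subjects or from AEs starting after 90 days.

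**Conclusion.** The gap is real and minor. It is a stated rule that gives the wrong classification in a definable case, not merely missing detail. The conclusion rests on two conditions: an AE starts in the 3 to 4 days between consent and infusion, and its later worsening stays on the same record. If sites always open a new post-dose record, nothing is lost. The number of subjects affected cannot be estimated and is probably very small. What is at stake is completeness of the by-arm AE tables, mainly for serious infection. Efficacy, the mortality analyses and the reporting of SAEs from consent are unaffected.

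**What to change.** In Phase 3 SAP 5.8.1, define a TEAE as an AE that begins on or after study drug administration, or that began before it and increased in severity or became serious or fatal on or after it, in either case within 90 days. For AEs with pre-dose onset that are ongoing at dosing, query the site for the date of worsening. Count the event as treatment-emergent unless the worsening is shown to precede dosing.

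The change is best made before the first Cohort 1 database lock. If it comes later, the second lock described in Phase 3 SAP 4.6, which updates all analyses on complete data, is the natural place, with the change labelled. Phase 2 has already been reviewed unblinded, so there the revised flag belongs at most in a labelled post hoc supplementary table.

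The cost is one sentence, a change to the flag, and a few site queries. The queries are needed because neither the AE record in Protocol 12.4 nor the planned AE listing names a date of severity change. Reported AE counts may rise slightly.

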### **5.8.2. Clinical Laboratory Parameters**

The following laboratory tests are performed at the Study Site/Clinic laboratories and recorded on the eCRF:

- Screening for tuberculosis
- Pregnancy
- SARS-CoV-2 test with RT-PCR
- Hematology: complete blood count + differential
- Chemistry: electrolytes, blood urea nitrogen, glucose, and CR
- Liver profile: AST, ALT, Alb, AlkP, Tbili, Dbili
- Lipid panel: Cholesterol, total; high-density lipoprotein (HDL) cholesterol; low-density lipoprotein (LDL) cholesterol (calculation); triglycerides; very low-density lipoprotein (VLDL) cholesterol (calculation)
- Urinalysis
- [REDACTED]

The following tests are performed by the central lab:

- Respiratory Viral Panel
- Anti-mavrilimumab Antibody

- [REDACTED]

Continuous laboratory data ([REDACTED], anti-mavrilimumab antibody, hematology, coagulation, chemistry, liver profile, and lipid panel) will be examined for trends using descriptive statistics of actual values and changes from baseline over time by treatment for the safety analysis set.

Shift tables will be produced for hematology and chemistry.

All laboratory results will be presented in by-subject listings.

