**Table 4: Schedule of Laboratory Assessments**

Activity / Parameter	Collection Detail	Collection Timepoints
CENTRAL LABORATORY		
Respiratory Panel	A/H3N2, A/H1N1pdm09, A/H7N9, A/H5N1, A, not typed, B, or other (specify); coronavirus – novel CoV, MERS CoV, other CoV (specify); RSV; adenovirus; bacteria; other infectious respiratory diagnosis (specify); clinical pneumonia	Screening
██████████	██████████	████████████████████ ████████████████████ ████████████████████
██████████ ██████████	████████████████████ ████████████████████ ████████████████████ ████████████████████ ████████████████████ ████████████████████	████████████████████ ████████████████████ ████████████████████
Anti-mavrilimumab antibody		Screening and the Discharge/UNS visit
Pharmacokinetic sample		Day 1 (before infusion and when infusion is complete), Days 3±1, 7±1, 15±2, 29+4 and at the Discharge/UNS visit
LOCAL LABORATORY		
Pregnancy test (women of child-bearing potential)	Urine or serum βhCG	Screening and at the Discharge/UNS visit; Day 90+14 is optional
██████████ ██████████		████████████████████ ████████████████████ ████████████████████
Hematology	Complete blood count + differential	Screening (up to 7 days prior to randomization), Days 3±1, 15±2, 29+4 and at the Discharge/UNS visit; Days 60+14 and 90+14 are optional
Coagulation	PT, PTT, and INR	
Chemistry	electrolytes, blood urea nitrogen, glucose and CR	
Liver Profile	AST, ALT, Alb, AlkP, Tbili, Dbili	

Activity / Parameter	Collection Detail	Collection Timepoints
Lipid Panel	Cholesterol, total; high-density lipoprotein (HDL) cholesterol; low-density lipoprotein (LDL) cholesterol (calculation); triglycerides; very low-density lipoprotein (VLDL) cholesterol (calculation)	Screening (up to 7 days prior to randomization) and at the Discharge/UNS visit
Urinalysis		Screening (up to 7 days prior to randomization) and Discharge/UNS visit; Day 29+4, Days 60+14 and 90+14 are optional
Tuberculosis		Optional at Screening - at Investigator's discretion South Africa only: TB testing required for all subjects at Screening
SARS-CoV-2	COVID-19	Screening* Days 1, 2, 3, 4, 5, 6, 7, 8, 15 ±2, 22 ±2, 29 +4 and Discharge/UNS are optional

Screening = up to 3 days prior to randomization

\*For SARS-CoV-2 testing (COVID-19), a positive test within 14 days of randomization is required. Sites that are unable to perform SARS-CoV-2 locally (at the clinical site or from another institution) may use Central Laboratory testing.

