#### **13.2.6. Other Analyses**

Pharmacokinetic parameters of mavrilimumab will be summarized. The presence of anti-drug antibodies will be explored. Parameters of mechanical ventilation, respiratory status, SOFA/qSOFA, and health care resource utilization (eg, days and/or length in hospital/ICU) will be summarized.

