## 1. INTRODUCTION

This Statistical Analysis Plan (SAP) describes the statistical analyses and data presentation to be performed for the Phase 3 part of the study KPL-301-C203 by Cohort. The efficacy endpoints are based on protocol amendment 6.0 dated November 8, 2021; while the data collection and visits might reflect previous versions of the protocol depending on the reconsent date. Selected outputs supporting efficacy of pooling Phase 2 and Phase 3 parts of the study by Cohort are covered under this SAP.

It contains definitions of analysis populations, derived variables, and statistical methods for the analyses of efficacy and safety. It is to ensure that the data listings, summary tables, and figures which will be produced, and the statistical methodologies that will be used, are complete and appropriate to allow valid conclusions regarding the study objectives.

The SAP will be finalized and approved prior to the clinical database lock (DBL) for the primary analyses when the last subject in Cohort 1 completes Day 29. A follow-up analysis will be conducted at the end of a 90-day safety follow-up period for all subjects. Cohort 1 and 2 will be analyzed separately. The database locks might be combined for the two cohorts as appropriate.

Analyses of pharmacokinetics (PK), Pharmacodynamics (PD), other biomarkers, and health care resource utilization are outside the scope of this SAP and will be addressed separately.

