### **4. GENERAL STATISTICAL CONSIDERATIONS**

Analyses described in this SAP will be conducted separately for each of the two cohorts. Treatment comparison will be primarily between each of the KPL-301 treatment arms (10 mg/kg, 6 mg/kg) vs placebo. Comparisons between the pooled KPL-301 treatment arms vs placebo will also be provided.

Summary statistics for continuous variables will include n (non-missing observations), mean, standard deviation, minimum, median, and maximum. Summary statistics for categorical variables will be presented in terms of frequencies and percentages based on the analysis set unless otherwise specified. In by-visit summary tables, only scheduled visits/timepoints will be summarized.

Time to event data will be summarized using the Kaplan-Meier (KM) method, which will include the estimated median, 25th percentiles, 75th percentiles, and their 95% confidence interval (CI). The CIs will be calculated using a log-log transformation. The event-free probability and its 95% CI will be calculated at days 4, 8, 15, 22, 29, 60 and 90 as appropriate using Greenwood's formula with a log-log transformation.

The 95% confidence interval (CI) of the difference in the proportion (KPL-301 – placebo) will be primary based on Cochran Mantel-Haenszel (CMH) test stratified by the randomization strata for binary (proportion or rate) endpoints.

All relevant subject data will be listed by cohort, treatment, subject and visit/time point including both scheduled and unscheduled visits.

Analyses of selected Day 90 efficacy endpoints will be conducted in the Day 90 analysis set in the Day 29 database lock. All Day 90 efficacy endpoints will be analyzed based on the ITT analysis set at the Day 90 database lock.

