## 6. CHANGES TO PLANNED ANALYSES FROM THE PROTOCOL

- The following other efficacy endpoints are out of scope for this SAP, and will be reported separately
  - [REDACTED]
  - [REDACTED]
  - [REDACTED]
  - [REDACTED]
  - [REDACTED]
  - [REDACTED]
- All randomized subjects will be included in the ITT analysis set.
- Summary of Remdesivir and Corticosteroids Before Day 29 are added
- For favorable Day 29 endpoints, death will be censored at Day 35 instead of Day 30 as specified in the protocol
- The main analyses for the first database lock of Cohort 1 will not use a fixed data cut-off date. Subject level Day 29 dates will be used instead.
  - Efficacy endpoints based on Day 29 will consider data through Day 29 window.
  - Non-efficacy parameters that involve data after Day 29 by definition, e.g., TEAE, CM, will only include data through Day 29 in the first database lock.
  - Lab summary tables will only include baseline; and lab shift tables will not be provided since only baseline lab data will be cleaned in the first DBL.

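### Phase 3 SAP 5.8.2 summarises anti-mavrilimumab antibody only as a continuous laboratory value plus a listing, so no planned summary table fixes the number of antibody-positive subjects

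*Combined protocol and SAP*

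**What the plan says.** - **Protocol 13.2.6** (and the synopsis): "The presence of anti-drug antibodies will be explored". No positivity rule, endpoint or method is attached.
- **Protocol Table 4:** samples for anti-mavrilimumab antibody are due at "Screening and the Discharge/UNS visit".
- **Phase 3 SAP 5.8.2:** the antibody is named among the data classed as continuous: "anti-mavrilimumab antibody, hematology, coagulation, chemistry, liver profile, and lipid panel) will be examined for trends using descriptive statistics of actual values and changes". Those changes are measured against baseline, and the summaries are shown by treatment and time point in the safety analysis set.
- **Phase 3 SAP Section 4** defines such a summary: "Summary statistics for continuous variables will include n (non-missing observations), mean, standard deviation, minimum, median, and maximum". Categorical variables get frequencies and percentages.
- **Phase 3 SAP 5.8.2** also states: "All laboratory results will be presented in by-subject listings". Its shift tables do not extend to ADA: "Shift tables will be produced for hematology and chemistry".
- **Phase 3 SAP Section 6:** at the first database lock, laboratory summaries are confined to baseline and shift tables are omitted, because later laboratory data will not yet have been cleaned.

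The readable SAP text has no count or percentage of ADA-positive subjects, no definition of positive or treatment-emergent ADA, and no denominator for it. The readable part of Section 6 declares no departure from the protocol on ADA.

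**The concern.** The question is one of presence, and the summary planned for it is that of a continuous measurement. To enter a mean, a negative sample has to be dropped or given a numeric code, and the SAP states neither rule. Whichever is used, the mean blends how many subjects are positive with how high their values are.

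At stake is whether the immunogenicity result of Phase 3 can be read. Protocol Section 4 lists severe hypersensitivity and immune complex disease among the important potential risks, and 12.2.1.3 makes anaphylaxis and severe hypersensitivity events of special interest. The number of subjects who develop antibody on each dose, kept apart from those who had it before dosing, is what would be set against those events. If that number is first counted from listings at the reporting stage, the definition of treatment-emergent positivity and the denominator may be chosen with the results by arm already known.

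**Working it through.** The documents give no ADA rate, sample size or power statement, so there is no plan figure to reproduce. The check is whether the number of positive subjects can be recovered from the six statistics in the planned table.

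**Inputs.** The list of statistics comes from Phase 3 SAP Section 4. The titres are assumed: 100 subjects per set, all negative at Screening, negatives coded 0. With every Screening value at 0, the post-dose value equals the change from baseline, so one calculation covers both planned summaries.

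- Set A positives: 80 once, 40 ten times, 50 ten times. Count 1 + 10 + 10 = 21.
- Set B positives: 80 once, and 10, 20 and 60 ten times each. Count 1 + 30 = 31.

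**Sums**
- A: 80 + 400 + 500 = 980. B: 80 + 100 + 200 + 600 = 980.

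**Sums of squares**
- A: 6,400 + 10 × 1,600 + 10 × 2,500 = 47,400.
- B: 6,400 + 10 × (100 + 400 + 3,600) = 47,400.

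**Mean and SD, the same for both sets**
- Mean = 980 / 100 = 9.8.
- SD = √[(47,400 − 980² / 100) / 99] = √[(47,400 − 9,604) / 99] = √381.8 = 19.54.

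| | n | Mean | SD | Min | Median | Max | Positive |
|---|---|---|---|---|---|---|---|
| A | 100 | 9.8 | 19.54 | 0 | 0 | 80 | 21 (21%) |
| B | 100 | 9.8 | 19.54 | 0 | 0 | 80 | 31 (31%) |

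The six statistics agree throughout and the incidences differ by 10 percentage points. The table limits the count but does not fix it. At least 980² / 47,400 = 20.3, so 21, subjects must be positive (Cauchy-Schwarz inequality). At most 49 can be, because a median of 0 in 100 non-negative values needs at least 51 zeros.

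**Other places in the plan that could supply the count**
- Shift tables cover hematology and chemistry only.
- The SAP's scope exclusion does not name ADA: "Analyses of pharmacokinetics (PK), Pharmacodynamics (PD), other biomarkers, and health care resource utilization are outside the scope of this SAP and will be addressed separately". Section 5.8.2 keeps ADA inside the SAP.
- Listings give each subject's result, but no count by arm, denominator or positivity rule.
- The same SAP handles another antibody test categorically: 5.3.2 tabulates anti-2019-nCoV as negative, positive, or not tested/missing.

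**The case against.** The strongest reply is that the planned output does contain the answer. Section 5.8.2 lists every laboratory result by subject, and Section 4 has subject data listed by cohort, treatment, subject and time point. The protocol promises only to explore presence, protocol 13.2.5 rules out formal analysis of safety endpoints, and a listing can serve an exploration. This stands against the inference that the plan cannot reveal presence of ADA at all. It can, through the listings. What remains is that no summary table counts positives and no rule for counting them is fixed in advance.

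Two further inferences also go too far:
- **That the dose arms could not be compared.** The continuous summaries are by treatment, so the arms stand side by side.
- **That baseline and post-dose antibody are merged.** Actual values and changes from baseline are both planned, and the listings show each subject's sequence. The missing element is a definition of treatment-emergent positivity.

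It may also be said that Section 4 would give frequencies if the assay reports positive or negative. The reporting format is not stated, so this is possible, but 5.8.2 names ADA as continuous, and the specific sentence would normally govern. For the same reason, it is an assumption that negatives carry no numeric value. Finally, the sentence in 5.8.2, the central-laboratory list and Section 6 all contain redactions, so a separate ADA output cannot be excluded. The visible classification would still need correcting.

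An example that matched only the means would not make the case, because the SD and maximum are also planned and could tell two such sets apart. The check above therefore ties all six statistics.

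**Conclusion.** The point holds in a limited form. The visible Phase 3 plan for ADA is a continuous summary and a listing, and the summary does not determine the number of positive subjects, which is what the protocol's question turns on. The illustration shows 21 against 31 positives per 100 behind one identical table. It rests on assumed titres with negatives coded 0. It shows that the count is not recoverable, and it does not predict an ADA rate in this trial.

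The consequence is minor. No efficacy conclusion, error rate or stated decision rule depends on ADA, and the count could still be made from listed data. The loss is pre-specification. The post-dose column in Table 2 also covers unscheduled visits, so a subject may have more than one post-dose sample, and others may have none. Which samples count, and over which subjects, should be settled beforehand.

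**What to change.** In Phase 3 SAP 5.8.2:

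1. Remove anti-mavrilimumab antibody from the continuous-laboratory sentence.
2. Add a categorical table by arm giving the number and percentage of subjects who are ADA-positive at baseline, and the number and percentage with treatment-emergent ADA, among subjects with an evaluable post-dose sample. Define treatment-emergent as negative at Screening and positive after dosing, or a rise above baseline by the assay's own criterion. State the number evaluable in each arm.
3. List or summarise any titres for positive samples only.

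For Cohort 1 the post-dose table belongs to the second database lock, since only baseline laboratory data are summarised at the first. Cohort 2 has a single lock (SAP 4.6), so its table falls there.

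The cost is a change of SAP wording and one categorical table in place of a continuous one, from samples already scheduled. No new data collection is needed.
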